## 9.7. Data Analysis

### 9.7.1. SCRI

#### 9.7.1.1. Primary Analysis

Descriptive statistics will be used to summarize the baseline characteristics of those who receive the COMIRNATY 2023-2024 Formula. Counts of each safety outcome of interest will be reported within pre-specified risk and control windows. Then, the observed incidence rates of the outcomes of interest will be estimated in the risk window and the control window. Among the individuals who experience an outcome of interest in either the risk window or the control window (but not both), an exact conditional Poisson regression model with the natural logarithm of the person-time as the offset will be used to calculate the relative incidence (rate ratio) and corresponding 95% confidence interval (CI) of the risk period relative to the control period. With the self-controlled design, whereby each individual serves as their own comparator, the analysis accounts for the factors that vary across but not within individuals (i.e., time-invariant covariates).

The results from the SCRI utilizing the Optum pre-adjudicated claims database will be presented in the interim report, while results from the SCRI utilizing the ORD will be presented in the final report.

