### 9.2.1. SCRI

#### 9.2.1.1. Inclusion Criteria

Patients must meet all of the following inclusion criteria to be eligible for inclusion in Phase 1 of the study:

1. Receive at least one dose of the COMIRNATY 2023-2024 Formula from the date of the COMIRNATY 2023-2024 product launch through 31 March 2024.
2. Age  $\geq$  6 months when receiving their first recorded dose of the COMIRNATY 2023-2024 Formula.
3. Have continuous medical and pharmacy insurance coverage in the 365 days prior to their vaccination date (as defined in [Section 9.2.3](#)), or since birth if the vaccination occurred at  $<$  1 year of age.
4. Experience a safety outcome of interest during a risk interval or control period (on or after vaccination, as defined in [Section 9.3.2](#)).
5. Do not experience the safety outcome of interest during the clean period (prior to vaccination, as defined in [Section 9.3.2](#)).

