#### **9.2.5. Follow-Up Period**

##### **9.2.5.1. SCRI**

In the SCRI analysis, follow-up for the risk period will begin upon (for the outcomes of anaphylaxis and convulsions/seizures) or one day after (for all other outcomes) receipt of the COMIRNATY 2023-2024 Formula ([Table 2](#)) and continue until the earliest of:

- Receipt of a COVID-19 vaccine other than the COMIRNATY 2023-2024 Formula;
- The end of the outcome-specific risk interval as defined in [Section 9.3.2](#);
- Disenrollment from the health plan, death, or the end of data collection.

After the outcome-specific pre-specified washout period following the risk interval, follow-up for the control period will begin and continue until the earliest of:

- Receipt of a COVID-19 vaccine other than the COMIRNATY 2023-2024 Formula;
- The end of the control period as defined in [Section 9.3.2](#);
- Disenrollment from the health plan, death, or the end of data collection.

Individuals will be followed for each safety outcome during both the risk and control periods, such that events observed during the risk period or washout period will not censor follow-up for the control period.

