### 9.3.2. Outcomes

In both the SCRI and cohort studies, the pre-specified safety outcomes of interest will include the following:

- ADEM
- Anaphylaxis
- Bell's palsy
- CVST
- Convulsions/seizures (non-febrile)
- Encephalomyelitis
- Glomerulonephritis
- Guillain-Barré syndrome
- Herpes zoster
- Immune-mediated myositis
- Immune thrombocytopenia
- Kawasaki disease
- Multi inflammatory syndrome (in children and adults)
- MS
- MI
- Myocarditis/pericarditis
- PE
- Stroke, hemorrhagic
- Stroke, ischemic
- Transverse myelitis

In addition, in Phase 2 of the study, the following pregnancy outcomes will be assessed in pregnant women or their infants, if sample size permits:

- Spontaneous abortion
- Stillbirth
- Preterm birth
- Major congenital malformations
- Small for gestational age

Code lists for the safety outcomes of interest are provided in [Annex 2 \(Appendix III\)](#). Corresponding site of care requirements are listed in Table 2. When possible, outcomes will be defined using a validated claims-based algorithm with high performance ([CBER, 2021](#)).

If a safety signal is detected in the interim report, then medical records will be retrieved for a subset of participants to confirm the presence of that study outcome. A safety signal that requires confirmation through medical record review will be defined as a rate ratio of > 3.0 and a corresponding P value of < 0.01 in the primary analysis of the SCRI design (details in [Section 9.7.1.1](#)). Additionally, medical record review may be conducted for analyses beyond the primary SCRI analysis if a safety signal (defined as a rate ratio of > 3.0 and a corresponding P value of < 0.01) is detected in the interim or final report. Medical records may also be retrieved for AESIs with estimates approaching the pre-specified safety signal threshold.

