### 9.3.2.1. Outcome-Specific Risk and Control Periods

The SCRI design ([Section 9.1.1](#)) requires that clean periods, risk intervals, washout periods, and control intervals be specified for every study outcome. The lengths of the clean periods and risk intervals are listed in [Table 2](#). The washout period for all outcomes will begin immediately after the end of the risk interval and continue for 30 days ([Akpandak et al., 2022](#)); the control period will follow the washout period and be equivalent in length to the risk interval. Interval lengths were determined based on prior vaccine literature, including COVID-19 vaccine studies conducted as part of the FDA’s Center for Biologics Evaluation and Research (CBER) Biologics Effectiveness and Safety (BEST) System ([Akpandak et al., 2022](#); [Barda et al., 2021](#); [CBER, 2021](#); [Joy et al., 2023](#); [Klein et al., 2021](#); [Liu et al., 2023](#); [Martin et al., 2021](#); [McCarthy et al., 2013](#); [Wack et al., 2021](#)).

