### 17.3. Appendix III – Safety Outcomes of Interest

All codes are ICD-10 diagnosis codes; all outcomes will be defined based on the presence of a single code unless otherwise specified. In order to qualify as an outcome, the outcome-specific codes must be identified during emergency department visits, inpatient hospitalizations, or outpatient visits, as detailed in [Table 2](#). Outpatient visits are defined through physician evaluation and management codes ([Section 17.2.3](#)).

\* Outcome codes marked with an asterisk are based on COVID-19 vaccine studies conducted as part of the FDA’s CBER BEST system.

- Acute disseminated encephalomyelitis (ADEM)\*
  - G04.00 – Acute disseminated encephalitis and encephalomyelitis, unspecified
- Anaphylaxis\*
  - T80.52XA – Anaphylactic reaction due to vaccination, initial encounter
  - T78.2XXA – Anaphylactic shock, unspecified, initial encounter
- Bell's palsy\*
  - G51.0 – Bell’s palsy
  - G51.8 – Other disorders of facial nerve
  - G51.9 – Disorder of facial nerve, unspecified
- Cerebral venous sinus thrombosis (CVST)
  - I67.6 – Nonpyogenic thrombosis of intracranial venous system
  - I63.6 – Cerebral infarction due to cerebral venous thrombosis, nonpyogenic
- Convulsions/seizures (non-febrile)
  - G40.001 – Localization-related (focal) (partial) idiopathic epilepsy and epileptic syndromes with seizures of localized onset, not intractable, with status epilepticus
  - G40.009 – Localization-related (focal) (partial) idiopathic epilepsy and epileptic syndromes with seizures of localized onset, not intractable, without status epilepticus
  - G40.011 – Localization-related (focal) (partial) idiopathic epilepsy and epileptic syndromes with seizures of localized onset, intractable, with status epilepticus
  - G40.019 – Localization-related (focal) (partial) idiopathic epilepsy and epileptic syndromes with seizures of localized onset, intractable, without status epilepticus
  - G40.101 – Localization-related (focal) (partial) symptomatic epilepsy and epileptic syndromes with simple partial seizures, not intractable, with status epilepticus

090177e1a5be86fe\Approved\Approved On: 19-Mar-2026 15:57 (GMT)

- G40.109 – Localization-related (focal) (partial) symptomatic epilepsy and epileptic syndromes with simple partial seizures, not intractable, without status epilepticus

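### In the SCRI, repeat codes for the same episode remove risk-window cases and add control-window cases, which biases the rate ratio downward for outcomes with coded follow-up visits

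*Protocol*

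**What the plan says.** All references are to the Protocol. Its Section 7 describes it as a combined protocol and statistical analysis plan, and Annex 1 lists no standalone documents, so the rule is fixed here.

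- **Cases analysed (9.7.1.1):** the exact conditional Poisson model is run "Among the individuals who experience an outcome of interest in either the risk window or the control window (but not both", with log person-time as the offset.
- **Earlier events (9.2.5.1):** "events observed during the risk period or washout period will not censor follow-up for the control period". Person-time in either window stops at death.
- **Incident-case rule (9.2.1.1, item 5):** "Do not experience the safety outcome of interest during the clean period". That period lies wholly before vaccination, or ends on the day of it.
- **Event definition (17.3):** "all outcomes will be defined based on the presence of a single code unless otherwise specified". Outpatient visits are identified by the evaluation and management codes in 17.2.3.
- **Windows (9.3.2.1):** "The washout period for all outcomes will begin immediately after the end of the risk interval and continue for 30 days", and "the control period will follow the washout period and be equivalent in length to the risk interval".
- **Signal (9.3.2):** record review in the interim report is triggered by a "rate ratio of > 3.0 and a corresponding P value of < 0.01 in the primary analysis of the SCRI design".

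No section requires a control-window event to be the person's first since vaccination.

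**The concern.** Section 9.1.1 gives the washout the task of keeping vaccine-related events out of the control period, and the clean period the task of keeping outcomes incident. The rules above do not secure either aim once an episode is coded more than once.

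- A person with onset in the risk window and a coded follow-up visit in the control window has an outcome in both, and is removed from the model.
- A person with onset in the washout and a coded follow-up visit in the control window has an outcome only in the control window, and enters as a control event.
- A person with onset in the control window has no later window in which a repeat code could remove them.

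The first two effects both lower the rate ratio, and nothing offsets them. This estimate is the Phase 1 primary analysis and the basis of the signal rule, so a real increase after vaccination could be understated and fail to trigger record review.

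**Working it through.** The Protocol states no event count, power or expected rate ratio, so there is no figure to reproduce. The check is of direction and size.

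**1. Which repeat codes matter.** With a 28-day risk interval (Days 1 to 28), the washout is Days 29 to 58 and the control window Days 59 to 86. A Day 28 case is dropped by a repeat code 31 to 58 days later, and a Day 1 case by one 58 to 85 days later. Repeat codes in the washout, or after Day 86, do not cause a drop.

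**2. Formula.** Let L be the window length, θ the true rate ratio, and the background onset rate constant. Let q be the share of risk-onset cases recoded in the control window, and w the same share for washout-onset cases.

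- Risk cases kept ∝ θL(1 − q)
- Control cases counted ∝ L + 30w
- Observed ratio = θ(1 − q) / (1 + 30w/L)

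L comes from Table 2 and the 30 days from 9.3.2.1. **q and w are not in the documents.** They are assumed equal and shown from 10% to 30%.

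| Outcome (L) | q = w = 10% | 20% | 30% |
|---|---|---|---|
| Myocarditis/pericarditis (21) | 0.79 | 0.62 | 0.49 |
| Pulmonary embolism (28) | 0.81 | 0.66 | 0.53 |
| Herpes zoster (30) | 0.82 | 0.67 | 0.54 |
| Bell's palsy, immune thrombocytopenia (42) | 0.84 | 0.70 | 0.58 |

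Example, L = 28 and 20%: 0.8 / (1 + 6/28) = 0.66. A true ratio of 3 reads 2.44, 1.98 or 1.59 across the 28-day row, and 2.36, 1.87 or 1.47 across the 21-day row.

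**3. Components.** At 20% and L = 21, dropping both-window cases alone gives 0.80. Washout carry-over alone gives 1/(1 + 6/21) = 0.78. Together they give 0.62.

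**4. Signal rule.** Assume θ = 4 and 10 expected control-window onsets, independent Poisson counts, and a two-sided exact binomial test. The chance of a ratio above 3.0 with P < 0.01 is about 80% with no recoding. For L = 21 it falls to about 29% at 20% recoding and 11% at 30%. For L = 42 it falls to about 42% and 23%.

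**5. First-code rule, non-recurrent outcomes.** Risk cases ∝ θL, washout-first cases are left out, and control cases ∝ L. The ratio is θ, a factor of 1.00.

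**6. First-code rule, recurrently coded outcomes.** If codes arrive at a constant rate k, the chance that the first falls in the risk window is 1 − exp(−kL). For the control window it is exp(−k(L + 30)) × (1 − exp(−kL)). A true ratio of 1 then reads exp(k(L + 30)). Non-febrile seizures have L = 22 (Days 0 to 21), a 42-day clean period and chronic epilepsy codes (G40.x) in their list. With one code per 90 days (assumed), the null ratio reads exp(52/90) = 1.78. With one per 180 days it reads exp(52/180) = 1.33.

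**7. Deaths (secondary).** A risk-window case who dies before the control window has no control time and contributes nothing. A fatal control-window case is kept, with shortened control time. With 28-day windows, death on the event day and assumed case fatality f, the null estimate solves (1 − f)(1 − θ)/(1 + θ) = fθ ln(1 + 1/θ). That gives about 0.86 at f = 10% and 0.60 at f = 30%.

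**The case against.** With equal windows, keeping only cases that fall in one window is a legitimate discordant-pair rule. If events in the two windows are independent new events, it does no harm. For rare events a ratio of 3 stays at 3.00, and at a 1% risk per window it reads (exp(0.03) − 1)/(exp(0.01) − 1) = 3.03. This stands: the bias comes from repeat codes of one episode, not from the exclusion as such. It also means that a first-code rule for all 20 outcomes would exchange one bias for another, as step 6 shows for seizures.

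Other points limit the scope:

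- Nine of the 20 outcomes in Table 2 accept no outpatient code. A repeat there needs a readmission or, for three of them, possibly an ED visit.
- Section 9.9 makes the cohort analysis primary for chronic outcomes, naming multiple sclerosis. Cohort follow-up ends at the outcome (9.2.5.2), so Phase 2 is free of this problem.
- Section 9.3.2 allows record review for estimates approaching the threshold. That is optional, and it depends on the estimate that is biased down.
- Section 9.7.1.1 also reports counts and rates by window, without the exclusion. These are no safeguard if every qualifying code counts. Their ratio would be θ/(1 + θq + 30w/L), which for θ = 3, L = 28 and 20% is 3/(1 + 0.60 + 0.21) = 1.65, lower than 1.98.

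A reader might infer that every washout-onset case becomes a control event, that any visit 30 or more days after onset removes a risk-window case, or that all SCRI ratios are pushed to null or below. The documents support none of these. Only a repeat code inside the control window counts. A true ratio of 3 falls below 1 only under extreme assumed shares: with L = 28, q = 50% and w = 60%, the factor is 0.30 and the ratio reads 0.91.

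**Conclusion.** The point holds for outcomes that do not normally recur within months but generate coded follow-up visits, chiefly those with inpatient and outpatient settings in Table 2. For these the direction is downward for any non-zero recode share.

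The exclusion of both-window cases is explicit. The washout effect is inferred from three provisions together: no censoring, a clean period before vaccination only, and the single-code definition.

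The size is conditional. With assumed recode shares of 10% to 30%, a true ratio of 3 reads about 2.4 to 1.5 for 21- and 28-day windows. The true ratio needed to read above 3.0 at 20% is about 4.8 for L = 21 and 4.3 for L = 42. The documents cannot say which shares apply. The effect is smaller for inpatient- or ED-only outcomes, and multiple sclerosis has the cohort as its primary analysis. The asymmetry for deaths is real, but its size rests wholly on assumed fatality.

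**What to change.** Amend Sections 9.2.5.1 and 9.7.1.1.

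- **Non-recurrent outcomes:** take the first qualifying code from the start of the risk interval and assign the case to the window in which it falls. Do not count a control-window code preceded by one in the risk or washout period. Remove the exclusion of both-window cases. The removal must come with the first-code rule, because counting both events would lower the ratio further.
- **Recurrently coded outcomes, notably non-febrile seizures:** restrict to new-onset cases by a longer code-free lookback within the 365-day baseline, or report both the first-code and the current rule. List in advance which outcomes fall in this group.
- **Deaths:** for cases who die, use the planned window lengths as person-time.
- **Sensitivity analysis:** report the current rule alongside, with the number of cases dropped for codes in both windows and the number of control events preceded by a washout code. These counts show how large q and w are.

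The cost is a few sentences and a rerun on data already held, plus an amendment with the prospective IRB approval that Section 10.3 requires. Genuine second episodes within the observation span are no longer counted. The final SCRI estimator will differ from the one planned for the interim report (milestone 30 June 2024), which is why the current rule should be kept as a sensitivity analysis. The change cannot alter the interim signal decision.

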## 6. MILESTONES

Milestone	Planned Date
Final study protocol	31 March 2024
Registration in the HMA-EMA Catalogues of RWD	To be determined
Start of data collection a	15 January 2024
Interim report b	30 June 2024
End of data collection c, d	31 August 2025
Final study report d	30 April 2026

a For studies with secondary data collection, the start of data collection is defined as the planned date for starting data extraction for the purposes of the interim analysis.

b The milestone date was chosen to inform decision making for the next adapted vaccine before Fall 2024. To meet this milestone, the data extraction for the interim reporting will include data through 15 January 2024.

c For studies with secondary data collection, the end of data collection is defined as the planned date on which the analytical dataset will be first completely available; the analytic dataset is the minimum set of data required to perform the statistical analysis for the final reporting.

d The sponsor may extend the study period. This revision, if needed, will be communicated to the FDA as a protocol amendment. Details on this contingency plan are provided in [Section 9.2](#).

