## 9.2. Setting

The source population for this study will consist of all individuals with at least one medical or pharmacy claim from 11 September 2023 through 31 March 2024. The end date of 31 March 2024 was chosen based on the assumption that vaccine uptake will be similar to uptake during the 2022-2023 season. During the 2022-2023 COVID-19 season, the end of March reflected the time when uptake of the bivalent booster was no longer increasing (i.e., most individuals who received the bivalent booster dose had done so prior to March 2023), and COVID-19 cases declined substantially from their peak ([CDC, 2020](#)).

Trends in COVID-19 vaccine uptake will be monitored until 30 June 2024 using the Centers for Disease Control and Prevention's (CDC) Weekly COVID-19 Vaccination Dashboard ([CDC, 2023d](#)), which publishes estimates of the proportions of children aged 6 months through 17 years and adults 18 years and older who have received a COVID-19 vaccine each week during the 2023-2024 season. If in the final week of reported data for June 2024 these estimates show vaccine uptake in either children or adults that is 1% or greater than the respective estimates reported for the first week of April 2024 (i.e., an increasing trend in COVID-19 vaccine uptake from the first week of April 2024 to the last week of June 2024), then the Sponsor will extend the end date of the accrual period into October 2024, and the updated source population will be reflected in the final study report. This date reflects the latest accrual date that still allows for meeting of the current study milestones. This revision, if needed, will be communicated to the FDA as a protocol amendment.

Each study design will have its own inclusion and exclusion criteria, as listed below.

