### **9.2.3. Vaccination Date and Cohort Entry Date**

In the Phase 1 SCRI analysis, the date of first vaccination with the COMIRNATY 2023-2024 Formula will be set as the vaccination date. For the analysis assessing individuals who receive more than one dose of the COMIRNATY 2023-2024 Formula, each vaccination with the COMIRNATY 2023-2024 Formula will be set as a new vaccination date.

In the Phase 2 cohort analysis, the cohort entry date will be the date individuals in the COMIRNATY group receive their first recorded dose of the COMIRNATY 2023-2024 Formula. For individuals in the comparator cohort, the cohort entry date will be set as the date of first qualifying healthcare encounter. Propensity score-matched comparators will also be matched on age group and calendar time. Regarding age, matching will be performed between patients within age groups (e.g., 6 months–4 years, 5–11 years, 12–17 years, 18–64 years, and  $\geq 65$  years). Regarding calendar time, patients will be matched within 14-day windows (e.g., 01 September 2023 to 14 September 2023, 15 September 2023 to 28 September 2023) in which individuals in the exposed cohort will have received vaccination with the COMIRNATY 2023-2024 Formula and individuals in the unexposed cohort will have had a healthcare encounter but no recorded vaccination with the COMIRNATY 2023-2024 Formula. Alternate calendar periods (e.g., one month) may be empirically explored.

For matched comparators, the cohort entry date will be the date within the matched 14-day calendar period on which they had a healthcare encounter.

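### The SCRI model has no calendar-time term while every control window comes after its risk window, so the net seasonal change in background incidence enters the rate ratio, and Section 9.9 does not say so

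*Protocol*

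**What the plan says.** - **Model (Protocol 9.7.1.1).** For people whose event falls in exactly one of the two windows, the section states: "an exact conditional Poisson regression model with the natural logarithm of the person-time as the offset will be used to calculate the relative incidence". It claims control only of factors that stay fixed within a person.
- **Windows (9.3.2.1).** "The washout period for all outcomes will begin immediately after the end of the risk interval and continue for 30 days". On what comes next, the same section adds that "the control period will follow the washout period and be equivalent in length to the risk interval". No outcome has a control window before vaccination.
- **Accrual (9.2.1.1).** Doses count "from the date of the COMIRNATY 2023-2024 product launch through 31 March 2024". For the interim report, Section 6 says that "the data extraction for the interim reporting will include data through 15 January 2024".
- **Phase 2 (9.2.3, 9.7.2.1).** "Regarding calendar time, patients will be matched within 14-day windows", and calendar month is also a term in the propensity score model.
- **Limitations (9.9).** The SCRI's weakness for chronic outcomes is named and its protection against time-fixed confounding is credited. Seasonal or other time-varying confounding of the SCRI is not mentioned.

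Section 7 calls the document a combined protocol and statistical analysis plan, and Annex 1 lists no standalone documents. The model is therefore stated here and not left to another plan.

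**The concern.** Self-control removes what is constant within a person. It does not remove what changes between the two windows for everyone. Because the control window is always the later one, a background rate that rises through autumn lowers the rate ratio, and a rate that falls toward spring raises it. The Phase 1 objective treats the control window as giving the expected rate, which requires a background that is level over the shift.

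The protocol gives some reason to doubt that. Section 9.2 says of the 2022-2023 season that, by the end of March, "COVID-19 cases declined substantially from their peak". One outcome follows COVID-19 circulation by definition: in Appendix III, multi inflammatory syndrome requires a COVID-19 code plus a second code. Calendar time is also controlled twice in Phase 2 and not at all in the SCRI.

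At stake are estimates pulled toward apparent protection for autumn vaccinees, which can hide a moderate increase in risk, and a confidence interval whose coverage worsens as events accumulate.

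**Working it through.** The protocol states no event count or power (Section 9.5), so there is no figure of its own to reproduce.

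**1. Window shift (Table 2 and 9.3.2.1).** For a risk interval of days a to b, with length L = b − a + 1, the control window is days b + 31 to b + 30 + L. The start-to-start shift is L + 30. The empty gap between the windows is 30 days for every outcome.

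| Risk interval | Examples | L | Control days | Shift |
|---|---|---|---|---|
| 0 to 1 | anaphylaxis | 2 | 32 to 33 | 32 |
| 1 to 21 | myocarditis/pericarditis | 21 | 52 to 72 | 51 |
| 0 to 21 | seizures | 22 | 52 to 73 | 52 |
| 1 to 28 | MI, PE, strokes | 28 | 59 to 86 | 58 |
| 1 to 30 | zoster | 30 | 61 to 90 | 60 |
| 1 to 42 | Bell's palsy, GBS, MS | 42 | 73 to 114 | 72 |

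**2. Rate ratio with no vaccine effect.** Assumptions, none of them given in the protocol:
- background f(t) = 1 + A·cos(2π(t − 15 January)/365), with A = 0.1, 0.2 or 0.3;
- 65% of doses from 11 September to the end of October, 25% in November and 10% from December to 31 March, evenly spread within each period;
- complete windows.

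With w(v) the share vaccinated on day v, for a 28-day outcome:

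null RR = Σ w(v)·Σ f(v + 1 … v + 28) ÷ Σ w(v)·Σ f(v + 59 … v + 86)

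Hand check for one date (1 October, A = 0.2), using window midpoints: the risk midpoint is 91.5 days before the peak, f ≈ 0.999; the control midpoint is 33.5 days before, f ≈ 1.168. The ratio is 0.999/1.168 ≈ 0.86; the day-by-day sum gives 0.857. For 15 February the same sum gives 1.19, the opposite direction.

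| A | Autumn-weighted | Uniform 11 Sep to 31 Mar |
|---|---|---|
| 0.1 | 0.954 | 1.016 |
| 0.2 | 0.914 | 1.031 |
| 0.3 | 0.879 | 1.045 |

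**3. Error rate of the exact test.** With equal windows and n events, the risk-window count is Binomial(n, p) with p = RR/(1 + RR), tested against 0.5. For A = 0.2, p = 0.914/1.914 = 0.477. Two-sided 5% rejection with no vaccine effect, autumn-weighted uptake:

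| Events | No season | A = 0.1 | A = 0.2 | A = 0.3 |
|---|---|---|---|---|
| 200 | 4.0% | 5.1% | 8.2% | 12.8% |
| 400 | 4.0% | 6.3% | 12.7% | 22.4% |
| 800 | 4.4% | 9.3% | 23.0% | 42.4% |

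Most rejections fall on the protective side (at 400 events and A = 0.2, 12.5 of the 12.7 points).

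**4. Power.** For a true RR of 1.3 at 400 events, p = 1.3/2.3 = 0.565 and power is 71%. At A = 0.2 the model targets 1.3 × 0.914 = 1.19, and power is 37%.

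**5. Signal rule (9.3.2: RR > 3.0 and P < 0.01).** With 40 events and a true RR of 4, the chance of meeting the rule is 73% without bias and 64% at a null RR of 0.91. With no vaccine effect, the chance of a false signal at 40 events stays below 0.04% in the autumn-weighted scenarios.

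**6. Interim cut.** For 42-day outcomes, data to 15 January 2024 give some control time only to doses by 3 November 2023 (15 January less 73 days), and a full control window only to doses by 23 September (less 114 days). Late-season doses, whose bias runs the other way, contribute nothing there.

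**The case against.** The strongest reply is that importance is not shown. The remark in Section 9.2 concerns COVID-19 cases and booster uptake in the previous season and is there to justify the accrual end date; it says nothing about the background incidence of MI, Guillain-Barré syndrome or most other outcomes. Amplitude, peak, uptake and event counts are all assumed, and one curve is applied to 20 dissimilar outcomes. Section 9.9 already warns of limited power, particularly in Phase 1. All of this stands: the missing term is certain, its size is not.

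Three stronger readings are tempting and are not supported:
- *The windows lie 32 to 72 days apart.* That is the start-to-start shift; the gap is 30 days throughout.
- *Any seasonal change becomes a vaccine effect.* Only the net change over vaccination dates does, and autumn and late-winter doses partly cancel, as the uniform-uptake column shows.
- *The study will raise or miss signals wholesale.* Step 5 shows a modest loss of sensitivity and almost no false signals under the protocol's own rule.

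Phase 2 covers the same 20 outcomes with calendar control in the same final report. That gives the reader a second estimate, but it does not correct the SCRI one, and the mandatory record-review trigger in Section 9.3.2 uses the interim SCRI result.

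Timing also matters. Version 3.0 is dated 18 March 2026, after the planned end of data collection (31 August 2025). Replacing the primary estimator or moving the signal rule now would be hard to defend and would break comparability with the interim report.

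**Conclusion.** The point holds in a limited form. Followed as written, Section 9.7.1.1 reports the net seasonal change in background incidence as part of the rate ratio, and Section 9.9 does not disclose it. For a 28-day outcome under the stated assumptions, the null RR is about 0.95 to 0.88 with autumn-weighted uptake and about 1.02 to 1.05 with uniform uptake. With autumn-weighted uptake, the nominal 5% test rejects about 6 to 22% of the time at 400 events and 9 to 42% at 800. The direction depends on when people were vaccinated.

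A reader might infer that the SCRI results are unusable or that error rates at least double throughout. The documents do not support that: at 200 events and 20% amplitude the exact test rejects about 8%, rare outcomes are dominated by random error, and the effect on the signal rule is small. The bias matters for the commoner outcomes in the final report, where moderate rate ratios and their intervals will be interpreted.

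**What to change.** In Section 9.7.1.1, keep the stated model. For the final ORD report, add a pre-specified calendar-time-adjusted SCRI estimate for outcomes with enough events, with the minimum number stated. Its offset would be log(person-time × background rate), where the rate is that of the same outcome by calendar month and age group in ORD members without recorded COMIRNATY 2023-2024. Pool months where rates are sparse. Where the background curve is captured correctly, the null RR returns to 1.00.

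Report this beside the unadjusted estimate and interpret the SCRI result in light of both. In Section 9.9, list seasonal confounding as an SCRI limitation.

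The cost is some programming on data already held. Background rates for rare outcomes will be noisy, and the background pool will include some vaccinees whose dose was not recorded, a misclassification that Section 9.9 already acknowledges.
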